9.1.6 Potential Immune Mediated Diseases (pIMDs)

Potential Immune Mediated Diseases (pIMDs), as defined in Section 10.5, will be collected throughout the study period, using the SAE reporting process.

9.1.7 12-lead ECG

A 12-lead ECG will be performed as described in the Schedule of Procedures to assess for evidence of cardiac adverse events. ECGs will be interpreted formally by a trained cardiologist.

9.1.8 Muscle biopsy

In the event of an extensive local inflammatory reaction, or evidence of systemic inflammatory or immune disease that requires further evaluation to understand the potential relationship to IMP, biopsy of the muscle in which the IMP was administered may be performed by an experienced operator. Volunteers will be informed about this potential procedure in the study informed consent document. If a muscle biopsy is indicated as a safety assessment, volunteers would provide informed consent for the procedure itself at that time.

9.1.9 Concomitant Medications

Concomitant receipt of other IMPs is prohibited during the study.

All medication ongoing at study entry will be documented. (See DCF instructions on DCC website)

During the study, information regarding concomitant medications and reasons for their use will be solicited from the study volunteers until six months after the injection. Ongoing concomitant medications will be recorded until end of study.

9.1.10 Routine laboratory parameters (Safety Labs)

Table 9.1.10-1 shows the laboratory parameters that will be measured routinely. The samples for these tests will be collected at Screening and all subsequent visits, as indicated in the Schedule of Procedures (Appendix A). Note that the Day 3 (+/- 1 day) visit does not include total bilirubin, alkaline phosphatase, albumin, creatine kinase and all tests listed in Table 9.1.10-1 as "Other". Also note that the Day 49 and Day 70 safety labs include Cardiac Troponin I only.

Laboratory	Test
Parameter	
Haematology	Haemoglobin, haematocrit, leukocytes, platelets, absolute neutrophil count, absolute lymphocyte count
Clinical	Sodium, potassium, creatinine, aspartate aminotransferase (AST),
Chemistry	alanine aminotransferase (ALT), total bilirubin, alkaline
	phosphatase, albumin, creatine kinase,
Urinalysis	Dipstick test for protein, blood glucose, ketones, esterase (leukocytes) and nitrite. If clinically significant abnormalities (e.g. blood, protein, leukocytes) are found on dipstick test, then further test(s) will be performed (e.g. microscopy, culture).
Other	C-reactive protein, cardiac troponin I, aPTT, INR, complement C3 and C4

 Table 9.1.10-1: Laboratory Parameters

9.1.11 Specific screening tests:

In addition to the tests listed in the table above, Screening Labs will include:

- Anti-AAV1 and anti-AAV2 antibodies
- PG9 antibodies
- Gamma glutamyl transferase (GGT)

In addition, volunteers will be screened to exclude the following diseases:

- Hepatitis B: positive for hepatitis B surface antigen (HBsAg)
- Hepatitis C: positive for hepatitis C antibodies (HCV antibodies)
- Active syphilis: confirmed diagnosis (i.e., positive RPR confirmed by TPHA)

9.2 Immunogenicity Assessments

9.2.1 PG9 antibody responses

- PG9 antibody activity in the volunteer serum and or plasma will be measured according to time points as indicated in the Schedule of Procedures (Appendix A) through the following: Binding antibodies to a gp120 protein known to bind to PG9 (rates and antibody titres)
- Neutralizing antibodies to a panel of viruses (rates, neutralization titres and breadth)

Anti-PG9 antibody activity will be measured in the volunteer serum and or plasma according to time points as indicated in the Schedule of Procedures

9.2.2 Laboratory assessments specific to AAV

Anti-AAV1 antibody Titres: titres to AAV1 capsid will be measured at screening/baseline and after rAAV-PG9DP administration, at time points specified in the Schedule of Procedures.

AAV1 Systemic Distribution of rAAV1-PG9DP: A DNA PCR assay using primers specific to the PG9DP insert will be performed on whole blood to determine if the vector genome is present in the systemic circulation after IM delivery at time points specified in the Schedule of Procedures.

9.2.3 Cellular Responses

IFN-g ELISPOT and/or Intracellular cytokine staining (ICS) will be performed to monitor the number of AAV-1 specific circulating T cells that can be stimulated to produce cytokines and other effector molecules at time points indicated in the Schedule of Procedures using AAV1 capsid peptide pools or other antigen preparations of AAV1.

Selected T cell responses may be further characterized using additional markers on the responding cells, such as markers for activation or homing to mucosal tissues (ICS).

At each time point indicated in the Schedule of Procedures using the procedure provided by the IAVI Human Immunology Laboratory, at least four vials of frozen peripheral blood mononuclear cells (PBMC) each containing approximately 10⁷ PBMC will be collected for immunogenicity analysis (ELISPOT,ICS) and/or quality control assays at the IAVI Human Immunology Laboratory. These samples will be shipped promptly, according to an agreed schedule.

9.2.4 PBMC, Serum and Plasma Storage

Samples of cryopreserved PBMC, plasma and serum will be stored as indicated in the SOP and may be used for the purposes of standardization, quality control and for future assays related to HIV vaccine research and development. These samples will be archived and the testing laboratories will be blinded to the volunteer's identity.

For the immunogenicity assessments, the laboratory personnel will be trained as necessary by the sponsor and provided with a written procedure manual. The sponsor will also provide specific instructions on reagents.

The samples described in Sections 9.2.2 and 9.2.3 will be sent from the CRC to the IAVI Human Immunology Laboratory and will be identified only by the volunteer's study ID number. The immunological testing will be performed at the IAVI Human Immunology Laboratory in accordance with IAVI standard operating procedures and standard reagents.

9.2.5 Muscle Biopsies

All volunteers in group D1 will undergo a muscle biopsy 3 months and 12 months after administration of IMP at one of the sites where the IMP was injected.

Microscopy and immunohistochemical staining will be performed on biopsy tissue to assess in situ parameters at the site of IMP administration, such as PG9 expression, inflammation, fibrosis.

AAV1 in situ presence of rAAV1-PG9DP: A DNA PCR assay using primers specific to the PG9DP insert will be performed on biopsy tissue to determine if the vector genome is present in the tissue at the site of IMP delivery.

9.3 Other Assessments

9.3.1 HLA Typing

Samples for HLA typing will be collected as specified at the time point specified in the Schedule of Procedures and may be analyzed as warranted.

9.3.2 HIV test

Samples will be tested at the time points indicated in the Schedule of Procedures (Appendix A). Further information is specified in Section 11.1 HIV Testing.

9.3.3 Screening Assessment

The screening assessment is a conducted by going through the Inclusion and Exclusion Criteria.

9.3.4 HIV Risk Assessment

Study staff will assess volunteers at time points indicated in Schedule of Procedures (Appendix A) for their past and current risk of acquiring HIV.

9.3.5 Social Impact Assessment

Each volunteer will have a social impact assessment administered at the time points specified in the Schedule of Procedures (Appendix A). This assessment is intended to assess the impact of trial participation on the volunteer's personal and professional life.

10.0 ADVERSE EVENTS

10.1 Definition

An adverse event (AE) is any untoward medical occurrence in a volunteer administered IMP and which does not necessarily have a causal relationship with the IMP. An AE can therefore be any unfavorable or unintended sign (including an abnormal laboratory finding), symptom, or disease, temporally associated with the use of the IMP whether or not related to the IMP.

Assessment of severity of all AEs, including expectedness and seriousness of AEs, is ultimately the responsibility of the Principal Investigator.

10.2 Assessment of Severity of Adverse Events

The following general criteria should be used in assessing adverse events as mild, moderate, severe or very severe at the time of evaluation:

Grade 1 (Mild): Symptoms causing no or minimal interference with usual social and functional activities

Grade 2 (Moderate): Symptoms causing greater than minimal interference with usual social and functional activities

Grade 3 (Severe): Symptoms causing inability to perform usual social and functional activities

Grade 4 (Very Severe): Symptoms causing inability to perform basic self-care functions OR Medical or operative intervention indicated to prevent permanent impairment, persistent disability, or death

Guidelines for assessing the severity of specific adverse events and laboratory abnormalities are listed in Appendix B, Adverse Event Severity Assessment Table.

10.3 Relationship to Investigational Medicinal Product

Assessment of relationship of an AE or SAE to IMP is the responsibility of the Principal Investigator or designee. All medically indicated and available diagnostic methods (e.g., laboratory, blood smear, culture, X-ray, etc.) should be used to assess the nature and cause of the AE/SAE. Best clinical and scientific judgment should be used to assess relationship of AE/SAEs to the IP and/or other cause.

The following should be considered:

- Presence/absence of a clear temporal (time) sequence between administration of the IMP and the onset of AE/SAE
- Presence/absence of another cause that could more likely explain the AE/SAE (concurrent disease, concomitant medication, environmental or toxic factors)
- Whether or not the AE/SAE follows a known response pattern associated with the IMP

The relationship assessment should be reported as one of the following:

Not Related: clearly explained by another cause (concurrent disease, concomitant medication, environmental or toxic factors, etc.).

Unlikely: more likely explained by another cause (concurrent disease, concomitant medication, environmental or toxic factors, etc.).

Possibly: equally likely explained by another cause but the possibility of the IMP relationship cannot be ruled out (e.g., reasonably well temporally related and/or follows a known IMP response pattern but equally well explained by another cause).

Probably: more likely explained by the IMP (e.g., reasonably well temporally related and/or follows a known Investigational Medicinal Product response pattern and less likely explained by another cause).

Definitely: clearly related and most likely explained by the IMP.

For the purpose of expedited safety reporting, all possibly, probably or definitely related SAEs are considered IMP-related SAEs.

10.4 Serious Adverse Events

An adverse event is reported as a "Serious Adverse Event" if it meets any of the following criteria (as per International Conference on Harmonisation [ICH] Good Clinical Practice [GCP] Guidelines):

- Results in death
- Is life threatening
- Results in persistent or significant disability/incapacity
- Requires in-patient hospitalization or prolongs existing hospitalization
- Is a congenital anomaly/birth defect or spontaneous abortion
- Any other important medical condition that requires medical or surgical intervention to prevent permanent impairment of a body function or structure

Elective surgery for pre-existing condition that did not increase in severity or frequency is not considered an SAE.

Serious Adverse Events (SAEs) should be reported to IAVI within 24 hours of the site becoming aware of the event, and sent to the Sponsor as described in the SOM.

To discuss IMP-related SAEs or any urgent medical questions related to the SAE, the site investigator should contact one of the IAVI Medical Monitors directly (see Contact List in the SOM).

The IAVI SAE Report Form should be completed with all the available information at the time of reporting and sent to the Sponsor as described in the SOM. The minimum data required in reporting an SAE are the study identification number, date of birth, gender, event description (in as much detail as is known at the time), onset date of event (if available), reason event is classified as serious, reporting source (name of Principal Investigator or designee), and relationship to the IMP as assessed by the investigator.

The Principal Investigator or designee is required to prepare a detailed written report with follow up until resolution or until it is judged by the Principal Investigator or designee to have stabilized.

The Principal Investigator or designee must notify the responsible Ethics Committee of all SAEs as appropriate. In case of IMP-related SAEs, the Sponsor will notify responsible regulatory authorities, Safety Review Board (SRB), and other study sites where the same IMP is being tested.

More details on SAE definitions and reporting requirements are provided in the SOM.

Serious Event Prior to Investigational Medicinal Product Administration

If a serious event occurs in the period between the volunteer signing the Informed Consent Form and receiving the study injection, the event will be reported using the SAE form and following the same procedures for SAE reporting, as indicated in Section 10.4. The timing of the event will be indicated by using the relevant checkbox on the SAE form.

10.5 Reporting Potential Immune-Mediated Diseases

Potential immune-mediated diseases (pIMDs) are a subset of AEs that include both clearly autoimmune diseases and also other inflammatory and/or neurologic disorders which may or may not have an autoimmune aetiology. These events are of special interest since they could potentially be caused by immune responses to the transgene. The investigator should report such adverse events within the same time limits (following confirmation of an AE as a pIMD; see last paragraph of this section below), and using the same CRF pages, as utilized for SAEs. The investigator will evaluate the occurrence of pIMDs at every visit/contact during the study. IAVI will also expect investigators to provide additional information about pIMD events. AEs to be reported and documented as pIMDs include:

Neuroinflammatory disorders: optic neuritis, cranial nerve disorders (including Bell's palsy), multiple sclerosis, demyelinating disease, transverse myelitis, Guillain-Barré syndrome, myasthenia gravis, encephalitis, neuritis.

Musculoskeletal disorders: systemic lupus erythematosus, cutaneous lupus, Sjögren's syndrome, scleroderma, dermatomyositis, polymyositis, myopathy, rheumatoid arthritis and juvenile rheumatoid arthritis, polymyalgia rheumatica or temporal arteritis, reactive arthritis, psoriatic arthropathy, ankylosing spondylitis, undifferentiated spondyloarthropathy.

Gastrointestinal disorders: Crohn's disease, ulcerative colitis or proctitis, celiac disease.

Metabolic diseases: autoimmune thyroiditis, Grave's or Basedow's disease, Hashimoto thyroiditis, insulin-dependent diabetes mellitus (IDDM), Addison's disease.

Skin disorders: psoriasis, vitiligo, Raynaud's phenomenon, erythema nodosum, autoimmune bullous skin diseases.

Others: autoimmune hemolytic anemia, thrombocytopenia, antiphospholipid syndrome, *vasculitis, pernicious anemia, autoimmune hepatitis, primary biliary cirrhosis, primary sclerosing cholangitis, autoimmune glomerulonephritis, autoimmune uveitis, autoimmune myocarditis/cardiomyopathy, sarcoidosis, Stevens-Johnson syndrome, Behçet's syndrome.

Injection site reactions: Grade 3 or 4 injection site reactions lasting more than 2 days.

*Vasculitis: Vasculitis, Diffuse vasculitis, leucocytoclastic vasculitis, polyarteritis nodosa, microscopic polyangiitis,Wegener's granulomatosis, anti-neutrophil cytoplasmic antibody positive vasculitis, Henoch-schönlein purpura, allergic granulomatous angiitis (Churg-Strauss disease), Kawasaki disease, Takayasu's arteritis, temporal arteritis (giant cell arteritis), renal vasculitis.

Medical judgement should be exercised in deciding whether other disorders/diseases have an autoimmune origin and should also be reported as described above, and this judgement is the investigator's prerogative. Whenever sufficient data exist to substantiate any of the diagnoses in the above list, the event must be reported as a pIMD. While the intent of pIMD reporting is to be inclusive, isolated nonspecific symptoms, which might (or might not) represent the above diagnoses, should be captured as AEs but not reported as pIMDs until the diagnosis can be defended.

10.6 Clinical Management of Adverse Events

Adverse events (AEs) will be managed by the clinical study team who will assess, provide first line of care as appropriate and refer to health care and treatment facilities as warranted. If any treatment/medical care is required as a result of the harm caused by the IMP or study procedures, this care will be provided free of charge.

If a volunteer has an AE and/or abnormal laboratory value that is known at the time of study injection, the specifications of Section 12.0 will be followed.

Volunteers will be followed until the AE resolves or stabilizes or up to the end of the study, whichever comes last. If at the end of the study, an AE (including clinically significant laboratory abnormality) that is considered possibly, probably or definitely related to the IMP is unresolved, follow-up will continue until resolution if possible and/or the volunteer will be referred.

10.7 Intercurrent HIV Infection

HIV infection cannot be directly caused by the IMP. If a volunteer acquires HIV through exposure in the community, the volunteer should have an Early Termination (ET) visit and offered referral to appropriate care and treatment facilities. The volunteer will be invited to enrol into a long term follow-up protocol for HIV infected volunteers, as described in Section 11.3.2.

Intercurrent HIV infection in study volunteers, although not considered an SAE, must be reported promptly to IAVI using the designated forms. However, medical conditions associated with the HIV infection that meet criteria for serious specified in the Section 10.4 of this Protocol (e.g., sepsis, *Pneumocystis jiroveci [carinii] pneumonia*, etc.) should be reported as SAEs using the SAE Report Form.

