			C &C1	8x10 ¹³ vg		2mL (1mL in each deltoid after drawing 0.5mL from each of 4 vials of IMP)
		D	1.2x10 ¹⁴ vg		3mL (1.5mL in each deltoid after drawing 0.5mL from each of 6 vials of IMP)	6 vials IMP
		D1	1.2x10 ¹⁴ vg		3mL (3 injections of 0.5mL each in each quadriceps, after drawing 0.5mL from each of 6 vials of IMP)	6 vials IMP
	Placebo	A & B	N/A	1.1 mL	1mL	1 vial excipient
		C &C1			2ml (1mL in each deltoid after drawing 1.0mL from each of 2 vials of excipient)	2 vials excipient
		D			3mL (1.5mL in each deltoid after drawing 1.0mL from each of 3 vials of excipient)	3 vials excipient
		D1			3mL (3 injections of 0.5mL each in each quadriceps, after drawing 0.5mL 6 times from a total of 3 vials of excipient)	3 vials excipient
DURATION OF STUDY PARTICIPATION	Volunteers will be screened up to 42 days before injection and will be followed for 12 months after the single administration. It is anticipated that it will take approximately 13 months to enrol the study.					
				tudy, volunteers will be asked to participate in a afety and PG9 expression for at least 4 additional		

RANDOMIZATION AND BLINDING	Volunteers will be randomly assigned IMP or placebo within each of the dose groups described in the study design table above depending on which group is enrolling. Study staff and volunteers will be blinded only with respect to the allocation of placebo or IMP. Blinding will not apply to the assignment of dosage levels.
EVALUATION FOR INTERCURRENT HIV INFECTION	Volunteers will be tested for HIV according to the Schedule of Procedures. Test results will be interpreted according to a pre-determined diagnostic algorithm. Should one or more serological HIV test(s) post vaccination be positive, a nucleic-acid-based HIV test will be performed to distinguish a natural HIV infection acquired through exposure in the community from serologic reactivity due to the PG9 antibody. HIV testing at additional time points may be performed upon the request of the volunteer and Principal Investigator or designee as medical or social circumstances warrant. To maintain blinding of study staff who have direct contact with the volunteers, HIV test results will be reported to the clinical team as "HIV- uninfected" or as "HIV-infected" (ONLY once intercurrent HIV infection is confirmed). Volunteers who acquire HIV infection during the study, despite counselling, will have an Early Termination visit conducted and be immediately referred for treatment and care.

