4.0 STUDY ENDPOINTS

4.1 Study Endpoints

4.1.1 **Primary Endpoints**

Safety and tolerability:

- **1.** Proportion of volunteers with moderate or greater reactogenicity (i.e., solicited adverse events) during a 7 day follow-up period after each injection
- 2. Proportion of volunteers with moderate or greater adverse events (i.e., unsolicited adverse events), including safety laboratory (biochemical, haematological) parameters, from the day of injection up to 168 days post injection
- 3. Proportion of volunteers with serious adverse events (SAEs) related to the IMP throughout the study period
- Proportion of volunteers in each group with potential Immune Mediated Diseases (pIMDs), defined as adverse events potentially caused by antigen-antibody complexes or immune responses directed to cells producing the transgene

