12.2 Withdrawal from the Study (Early Termination)

Volunteers may be withdrawn from the study permanently for the following reasons:

- 1. Volunteers may withdraw from the study at any time if they wish, for any reason
- 2. The Principal Investigator or designee has reason to believe that the volunteer is not complying with the protocol
- 3. If the Sponsor decides to terminate or suspend the study
- 4. If a volunteer becomes infected with HIV (through exposure in the community)

If a volunteer withdraws or is withdrawn from the study, all termination visit procedures will be performed according to the Schedule of Procedures (Appendix A) when possible. Every effort will be made to determine and document the reason for withdrawal.

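### Early Termination after HIV infection, or permitted withdrawal for non-compliance, leaves a dosed volunteer with no scheduled SAE/pIMD contact, although collection is meant to run for the whole study

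*Protocol*

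**What the plan says.** **What triggers Early Termination (ET).** For a volunteer who acquires HIV in the community, Protocol 10.7 says that "the volunteer should have an Early Termination (ET) visit and offered referral to appropriate care and treatment facilities". The synopsis (evaluation for intercurrent HIV infection) is firmer: such volunteers "will have an Early Termination visit conducted and be immediately referred for treatment and care". Appendix A note 3, attached to the Day 168 HIV test, also directs an ET visit and refers to the Study Operations Manual for details.

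**Withdrawal.** Section 12.2 opens with "Volunteers may be withdrawn from the study permanently for the following reasons". Its list includes HIV infection and also this: "The Principal Investigator or designee has reason to believe that the volunteer is not complying with the protocol". Appendix A note 1 makes the ET procedures those of the last visit. Nothing is scheduled after that.

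**What the endpoints need.** Primary endpoint 3 in 4.1.1 is "Proportion of volunteers with serious adverse events (SAEs) related to the IMP throughout the study period". Section 9.1.5 collects SAEs over the entire study. Endpoint 4 (pIMDs) names no window, but 9.1.6 supplies one: pIMDs "will be collected throughout the study period, using the SAE reporting process". Section 5.1 sets follow-up at 12 months after the single administration, which is Day 336 in Appendix A.

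**Substitute follow-up.** Section 10.7 adds: "The volunteer will be invited to enrol into a long term follow-up protocol for HIV infected volunteers, as described in Section 11.3.2". Despite its heading, 11.3.2 covers only referral and provision of antiretroviral therapy. The general long-term study (5.1, 7.9) is offered, not required, and has its own consent.

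**The concern.** Taking a volunteer off a repeated-dose product at least limits further exposure. Here there is one injection on Day 0, and 2.1 hypothesises PG9 expression for at least 12 months. Ending participation therefore removes no exposure; it removes only the chance to see what follows.

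Followed as written, the ET instruction makes primary safety data go missing because of an event after dosing, not because the volunteer declined further contact. Section 2.7 singles out immune responses to the expressed protein as needing close evaluation and calls long-term safety an important part of development. A late pIMD or related SAE in a terminated volunteer would have no scheduled route into endpoints 3 and 4. Section 7.7 provides replacement only for volunteers discontinued before receiving product, so a dosed volunteer who leaves is not replaced. With 3 active recipients in most groups, each one matters.

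**Working it through.** **1. The instructions side by side**

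| Place | Trigger | Force |
|---|---|---|
| Synopsis | HIV infection | *will* have ET |
| 10.7 | HIV infection | *should* have ET |
| Appendix A note 3 | HIV infection | directive to conduct ET |
| 12.2 | HIV infection; non-compliance | *may* be withdrawn, permanently |

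The force differs for the same event. Non-compliance appears only under *may*.

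**2. What remains after ET**

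- Appendix A: no visit or contact.
- 10.6: follow-up of an AE already present.
- 10.7: serious HIV-associated conditions are to be reported as SAEs, with no time limit and no scheduled contact to find them.
- HIV follow-up protocol: by invitation, and not described where 10.7 points.
- Long-term study: offered on completion of this study in 5.1, but to study volunteers without that condition in 7.9. Nothing says that its data feed endpoints 3 and 4.

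No sentence says that SAE/pIMD collection stops at ET. None provides for it to continue.

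**3. Follow-up forgone**

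Scheduled post-dose HIV tests fall on Days 168 and 336 (Appendix A).

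- Detection at Day 168: (336 − 168)/336 = 50% of SAE/pIMD follow-up. Endpoint 1 (7 days) and endpoint 2 (to Day 168) are already complete.
- Detection at Day 336: (336 − 336)/336 = 0%.
- Sections 10.7 and 11.1 and the synopsis also allow infection to be found between scheduled tests. For scale, ET at an assumed Day 84 forgoes (336 − 84)/336 = 75%, and at an assumed Day 252, (336 − 252)/336 = 25%.

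**4. Effect on the stated precision**

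Section 14.2 gives exact (Clopper-Pearson) 95% upper bounds with zero events. The two-sided form is 1 − 0.025^(1/n):

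| n | Computed | Stated |
|---|---|---|
| 3 | 70.8% | 70.8% |
| 12 | 26.5% | 26.5% |
| 15 | 21.8% | 21.8% |
| 18 | 18.5% | 18.5% |

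All four reproduce, so there is no arithmetic error behind this point. Now assume that one active recipient leaves the denominator:

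- 3-active group: 1 − 0.025^(1/3) = 70.8% becomes 1 − 0.025^(1/2) = 84.2%.
- Group D1 (4 active): 1 − 0.025^(1/4) = 60.2% becomes 70.8%.
- All active pooled, path through C1 (18 active): 18.5% becomes 1 − 0.025^(1/17) = 19.5%.

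**The case against.** The strongest reply is that this is a rare event and the gap is inferred. At most 24 men are enrolled, 5.4 excludes those with recent HIV risk behaviour, and no infection or withdrawal rate is given. At a scheduled Day 168 detection two of the four primary endpoints are complete and only the Day 252 and Day 336 visits remain for most groups. The Study Operations Manual, which is not at hand, may give more detail. The safety analysis is descriptive. All of this stands and limits the size of the point. It does not supply a contact after ET.

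Some stronger readings are tempting but not supported:

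- *Non-compliance leads automatically to ET.* Section 12.2 only permits withdrawal.
- *The protocol orders collection to stop at ET.* It does not say so; that is inferred from permanent withdrawal and the empty schedule.
- *ET contradicts 10.6.* That section says "Volunteers will be followed until the AE resolves or stabilizes or up to the end of the study, whichever comes last", but it concerns an AE already present. It promises no surveillance for new events and, if anything, protects observation of known ones after ET.
- *A terminated volunteer cannot enter the long-term study.* Section 5.1 suggests this, but 7.9 sets no completion condition. The two need reconciling.
- *A volunteer found infected on the Day 0 sample would be dosed and terminated within days.* Section 6.2 lists HIV testing and counselling before the injection, and 7.3 includes counselling once results are available. Nothing says that dosing proceeds with the result pending.

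How a terminated volunteer enters a proportion, and how PG9 samples taken after infection are handled, are matters for the analysis plan; their absence here is no finding.

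**Conclusion.** The point holds in a limited form. The synopsis, 10.7 and Appendix A note 3 direct ET for HIV infection after an injection that cannot be withdrawn, and 12.2 permits permanent withdrawal for HIV infection or non-compliance. The protocol schedules no later SAE/pIMD contact, while endpoint 3, 9.1.5 and 9.1.6 require collection over the whole study. The optional follow-up routes reduce the gap but do not close it.

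The expected number affected is small and cannot be calculated from the document. For one affected volunteer, detection at Day 168 costs half of the planned SAE/pIMD follow-up. The move from 70.8% to 84.2% is a worst case for a single group: it assumes that the man is an active recipient, that his group has 3 active recipients, and that he leaves the denominator entirely despite the months already observed. Pooled over 18 active recipients, the same loss moves the bound only from 18.5% to 19.5%. The change is worth making because the lost data are primary safety data and the remedy is cheap.

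**What to change.** 1. In 12.2, separate withdrawal of consent from the other reasons. State that an injected volunteer who agrees continues SAE and pIMD collection to Day 336, and AE collection to Day 168, at the time points already scheduled, by telephone if he prefers. Referral for care stays as it is.
2. Align the synopsis, 10.7, 12.2 and Appendix A note 3, which now variously say *will*, *should*, *may* and a plain directive for the same event.
3. Repair the reference from 10.7 to 11.3.2: either describe the HIV follow-up protocol there or cite where it is described.
4. Reconcile 5.1 (and the matching synopsis text) with 7.9, so that these volunteers are also offered the long-term study.

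The cost is protocol and consent wording and a few extra contacts for the rare affected volunteer, some of them with men who comply poorly. No new procedure is needed.
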